## 1.4.3 Efficacy of Acalabrutinib

Preliminary efficacy data as of 03 April 2017 have been evaluated for subjects with CLL, including subjects with R/R CLL (N=134), treatment-naive subjects (N=99), ibrutinibintolerant subjects (N=33), and subjects with Richter's syndrome or PLL transformation (N=29). The ORRs for the 4 populations were 96.9%, 99.0%, 80.6%, and 37.0%, respectively. Efficacy data through 28 February 2017 are also available on the first 124 sequentially enrolled subjects with R/R MCL who were treated with acalabrutinib monotherapy. With a median follow-up of 15.2 months, the ORR was 80.6%, with CR in 39.5% of subjects. See the acalabrutinib IB for details.

## 1.5 BENEFIT/RISK OF ACALABRUTINIB

Acalabrutinib is a potent, orally administered small-molecule inhibitor of BTK. Preliminary efficacy and safety data from ongoing studies suggest that acalabrutinib is well tolerated and has robust activity as monotherapy and combination therapy.

## 2.0 STUDY OBJECTIVES

## 2.1 PRIMARY OBJECTIVE

To characterize the safety profile of acalabrutinib and pembrolizumab in subjects with hematologic malignancies.

## 2.2 SECONDARY OBJECTIVE

To evaluate the activity of acalabrutinib and pembrolizumab as measured by response rate, duration of response, progression-free survival, overall survival, and time to next treatment.

## 2.3 EXPLORATORY OBJECTIVES

# 3.0 STUDY DESIGN

This is a Phase 1b/2, open-label, nonrandomized study that will be conducted in 2 stages. In the first stage, Part 1 of the study will determine the safety and preliminary efficacy of acalabrutinib and pembrolizumab in a limited group of B-cell malignancies. In the second stage, Part 2 allows for possible expansion cohorts into a wider range of B-cell malignancies, and Part 3 (enrolled concurrently with Part 2) will evaluate the combination in subjects with myelofibrosis (see Figure 4).

#### Part 1

Six subjects will be enrolled to receive acalabrutinib in combination with pembrolizumab. If the combination is safe with  $\leq$ 1 DLT (6-week observation period) in the first 6 subjects, the cohort will be expanded up to 24 subjects to obtain additional safety information and to assess the efficacy of the combination.

Part 1 of the study will include adult subjects with the following disease types:

- Non-GCB DLBCL
- FL
- CLL/SLL

#### Part 2

Part 2 consists of expansion groups of up to 30 subjects per histology provided the safety and efficacy results from Part 1 of the study indicate that further evaluation of the combination is warranted. The possible expansion groups for Part 2 could include adult subjects with the following disease types:

- Non-GCB DLBCL
- GCB DLBCL
- Richter syndrome
- MCL

- iNHL
  - o FL
  - o WM
  - o CLL/SLL
- MM
- Other B-cell malignancy (including but not limited to: Hodgkin's lymphoma, Burkitt lymphoma, marginal zone lymphomas, mediastinal large B-cell lymphoma, and hairy cell leukemia)

Under Amendment 3 of this protocol, subjects with MCL or iNHL (including FL, WM, and CLL/SLL) are no longer enrolled. Under Amendment 4, subjects with RS are no longer enrolled.

## Part 3

Part 3 includes up to 30 subjects with primary MF, post-polycythemia vera MF, or post-essential thrombocythemia MF with thrombocytopenia or anemia. Part 3 will run in parallel with Part 2. Subjects with MF will receive a run-in of 6 weeks of acalabrutinib alone. Subjects who are demonstrating a clinically meaningful response, in the opinion of the investigator, may continue on acalabrutinib monotherapy; those who are not will be treated with combination therapy with acalabrutinib and pembrolizumab.

In Part 3, safety and response data will be reviewed after the initial 12 subjects have completed 24 weeks of treatment (i.e., the Week 25 visit) or have discontinued treatment before Week 25. The first 12 subjects will be evaluated regardless of the length of treatment with acalabrutinib alone or in combination with pembrolizumab. If <2 subjects who received acalabrutinib monotherapy or the combination with pembrolizumab have achieved a response of "clinical improvement" or better (see Table 9), the MF group will not be expanded. The decision to expand the study is multifactorial and will take into consideration the nature and quality of response, safety, and evolving competitive landscape. If the safety and response data indicate that further evaluation is warranted, up to 18 additional subjects with MF (for a total of up to 30 subjects) will be treated on the same adaptive regimen as was given to the first 12 subjects.

Under Amendment 3 of this protocol, Part 3 is closed to enrollment.

#### All Parts

Treatment with acalabrutinib may be continued until disease progression or an unacceptable drug-related toxicity occurs as defined in the protocol. Treatment with acalabrutinib can continue until the end of trial, defined as 48 months after the last subject is enrolled. Subjects who are still on treatment at the end of the study and deriving clinical benefit from acalabrutinib treatment may be eligible to enroll in a separate rollover study of acalabrutinib monotherapy. In the event that a rollover or safety extension study is available at the time of the final data cutoff and database closure, subjects who remain in Study ACE-LY-005 may be transitioned to such a study. Once all active subjects are eligible for and move to a rollover or safety extension study would ensure treatment continuation, with visit assessments per the rollover or extension protocol. Any subject who would be proposed to move to a rollover or safety extension study would be asked to sign an Informed Consent Form (ICF) for the rollover or safety extension study.

Treatment with pembrolizumab may continue for 24 months (103 weeks) from first dose of pembrolizumab, provided subjects are tolerating the drug and not progressing. In addition, pembrolizumab treatment can end for subjects with confirmed CR (or sCR for MM) if treatment has been administered for at least 24 weeks and 2 doses of pembrolizumab have been administered after confirmation of CR/sCR. Subjects who have **confirmed** progressive disease will come off treatment. Note: If there is uncertainty regarding whether there is cancer progression, the subject may continue study treatment and remain under close observation (e.g., evaluated at 4- to 8-week intervals) pending confirmation of progression. In particular, transient worsening of disease during temporary interruption of study therapy (e.g., for drug-related toxicity or intercurrent illness) may not indicate disease progression. In such circumstances, and if medically appropriate, subjects may resume therapy and relevant clinical, laboratory, and/or radiographic assessments should be done to document whether tumor control can be maintained or whether actual disease progression has occurred.

All subjects will have bone marrow biopsy, hematology, chemistry, thyroid, and urinalysis safety panels performed at screening. Once dosing commences (Day 1), all subjects will be evaluated for safety, including serum chemistry, hematology, and thyroid function tests, once weekly for the first 8 weeks, followed by a Week 10 visit and then every 3 weeks

thereafter (every 6 weeks thereafter for thyroid function tests) through Week 103. For subjects who discontinue pembrolizumab at Week 103, the Week 103 visit will be followed by Week 106 and Week 109 visits, at which time, the investigator will determine eligibility to continue single-agent acalabrutinib treatment. Subjects remaining on study treatment after Week 103 will have a Week 103 and Week 115 visit, and then visits for safety and tumor response assessments every 24 weeks starting at Week 127 through 3 years (for subjects with CLL/SLL histologies) or 5 years (for subjects with non-CLL/SLL histologies [i.e., DLBCL/Hodgkin lymphoma]), and then every 52 weeks thereafter (all histologies).

[figure not shown]
Subjects who permanently discontinue pembrolizumab at any time during study participation must have a minimum of 2 consecutive study visits, 3 weeks apart, after the last dose of pembrolizumab for safety evaluation. The study visits will be scheduled as follows:

- For all subjects except MM and CLL subjects
  - If a subject discontinued pembrolizumab prior to completing 37 weeks on study and is on acalabrutinib alone, study visits will be held every 3 weeks until Week 37. After Week 37, study visits will be held every 12 weeks.
  - If a subject discontinued pembrolizumab after completing 37 weeks on study and is on acalabrutinib alone, 2 consecutive study visits will be held 3 weeks apart (e.g., Week 40 and 43), after which study visits will be held every 12 weeks.
  - It is acknowledged that the discontinuation timepoint of pembrolizumab (if applicable) is unique per subject. To synchronize the every 12-week study visit schedule with the radiologic tumor assessment schedule, the first 2 study visits after pembrolizumab discontinuation should be 3 and 6 weeks after pembrolizumab discontinuation and then scheduled to align with the nearest radiological timepoint.
- For CLL subjects
  - If a subject discontinued pembrolizumab prior to completing 37 weeks on study and is on acalabrutinib alone, study visits will be held every 3 weeks until Week 37. After Week 37, study visits will be held every 12 weeks.
  - If a subject discontinued pembrolizumab after completing 37 weeks on study and is on acalabrutinib alone, study visits will be held every 12 weeks.
  - It is acknowledged that the discontinuation timepoint of pembrolizumab (if applicable) is unique per subject. To synchronize the every 12-week study

visit schedule with the radiologic tumor assessment schedule, the first study visit should be scheduled to align with the nearest radiological timepoint.

In addition, subjects who permanently discontinue pembrolizumab for any reason (e.g., pembrolizumab toxicity, AE, or completing the 103-week course of pembrolizumab) and remain on acalabrutinib alone at any time during study participation must have a thyroid test done every 6 weeks for 6 months after pembrolizumab discontinuation. Thyroid testing may be discontinued at 6 months if 1) testing that was performed at 6 months was normal and 2) testing that was performed 6 weeks prior to the 6-month timepoint was normal (for a total of 2 consecutive normal test results). Otherwise, thyroid testing will continue as scheduled until 2 consecutive normal test results.

Refer to Appendix 5 and Appendix 6 for a comprehensive list of study assessments and their timing.

## Figure 4 Study Schema

ACP-196=acalabrutinib; BID=twice per day; CLL/SLL= chronic lymphocytic leukemia/small lymphocytic lymphoma; DLT=dose-limiting toxicity; FL= follicular lymphoma; GCB=germinal center B-cell diffuse large B-cell lymphoma; iNHL=indolent non-Hodgkin lymphoma; IV=intravenous; MF=myelofibrosis (per Amendment 3, Part 3, MF was not opened for this study); MM=multiple myeloma; non-GCB DLBCL=non-germinal center B-cell diffuse large B-cell lymphoma; PO=oral; Q3W=every 3 weeks; RS=Richter's syndrome (under Amendment 4, subjects with RS are no longer enrolled); WM=Waldenström macroglobulinemia.

[figure not shown]
## 3.1 STUDY PARAMETERS

## 3.1.1 Safety Parameters

The safety of acalabrutinib and pembrolizumab will be characterized by the type, frequency, severity, timing of onset, duration, and relationship to study drug(s) of any treatment-emergent AEs or abnormalities of laboratory tests; SAEs; ECIs, or AEs leading to discontinuation of study treatment.

For consistency of interpretation, AEs will be coded using the Medical Dictionary for Regulatory Activities (MedDRA), and the severity of AEs and laboratory abnormalities will be graded using the Common Terminology Criteria for Adverse Events (CTCAE), Version 4.03 or higher. Standard definitions for seriousness will be applied (see Section 6.1).

# 3.1.2 Pharmacodynamic and Biomarker Parameters

## 3.1.3 Efficacy Parameters

Standardized response and progression criteria have been established for B-cell malignancies including WM (Bladé 1998; Durie 2006; Hallek 2008; Owen 2013; Tefferi 2013; Cheson 2014); assessments of acalabrutinib and pembrolizumab efficacy in this study will be based on these criteria. Efficacy endpoints will include:

- ORR
- Duration of response
- Progression-free survival
- Overall survival
- Time-to-next treatment

For Part 3 subjects with MF, an overall response will be defined as clinical improvement or better (clinical improvement, PR, or CR) see Table 9. An additional analysis will evaluate

response when defined as CR + PR only. Under Amendment 3 of this protocol, Part 3 is closed to enrollment.

## 3.2 RATIONALE FOR STUDY DESIGN AND DOSING REGIMEN

As described in Section 1.4, acalabrutinib is currently being evaluated in a Phase 1/2 study in subjects with CLL (ACE-CL-001). In this study, subjects have received oral dosages of 100 to 400 mg QD and 100 to 200 mg BID of acalabrutinib. All tested dose levels have been well tolerated and, to date, no DLTs have been observed. Robust clinical responses have been observed with dosages as low as 100 mg QD. Preliminary PK data from ACE-CL-001 suggests a plateauing of exposure after 250 mg QD. PD results from this study also show 100 mg BID has the highest BTK occupancy at 24 hours of all the regimens evaluated. Therefore, 100 mg BID maintains full target coverage over 24 hours, while lowering the Cmax and AUC of acalabrutinib suggesting this regimen is preferred when acalabrutinib is being administered with other agents to lower the potential risk of drug-drug interactions. Therefore, based on PK/PD and efficacy results of the Phase 1/2 study, a 200-mg total daily dose, administered 100 mg BID, will be evaluated in this protocol.

Because acalabrutinib has not yet been evaluated in subjects with MF, an adaptive regimen will be used in Part 3. Preliminary data in CLL suggest that responses to acalabrutinib occur rapidly; in study ACE-CL-001, some subjects obtained PRs after only 2 cycles (8 weeks) of therapy. Thus, subjects in Part 3 will receive at least 6 weeks run-in with acalabrutinib alone before beginning combination therapy with pembrolizumab. The adaptive dosing regimen allows for the reasonable possibility that robust activity will be seen in MF using acalabrutinib as a single agent, while providing combination therapy of acalabrutinib plus pembrolizumab for subjects who do not show a clinically meaningful response to acalabrutinib alone. Under Amendment 3 of this protocol, Part 3 is closed to enrollment.

The dose of pembrolizumab planned to be studied in this trial is 200 mg Q3W. The dose recently approved in the United States and several other countries for treatment of melanoma subjects is 2 mg/kg Q3W. Information on the rationale for selecting 200 mg Q3W is summarized below.

KEYNOTE-001 was an open-label Phase 1 study conducted to evaluate the safety, tolerability, PK and PD, and anti-tumor activity of pembrolizumab when administered as monotherapy. The dose escalation portion of this trial evaluated 3 dose levels, 1 mg/kg, 3 mg/kg, and 10 mg/kg, administered every 2 weeks (Q2W) and dose expansion cohorts evaluated 2 mg/kg Q3W and 10 mg/kg Q3W in subjects with advanced solid tumors. All dose levels were well tolerated and no DLTs were observed. This first-in-human study of pembrolizumab showed evidence of target engagement and objective evidence of tumor size reduction at all dose levels. No MTD has been identified. In addition, 2 randomized cohort evaluations of melanoma subjects receiving pembrolizumab at a dose of 2 mg/kg versus 10 mg/kg Q3W have been completed, and 1 randomized cohort evaluating 10 mg/kg Q3W versus 10 mg/kg Q2W has also been completed. The clinical efficacy and safety data demonstrate a lack of important differences in efficacy or safety profile across doses.

An integrated body of evidence suggests that 200 mg Q3W is expected to provide similar response to 2 mg/kg Q3W, 10 mg/kg Q3W and 10 mg/kg Q2W. Previously, a flat pembrolizumab exposure-response relationship for efficacy and safety has been found in subjects with melanoma in the range of doses between 2 mg/kg and 10 mg/kg. Exposures of 200 mg Q3W are expected to lie within this range and will be close to those obtained with the 2 mg/kg Q3W dose.

A population PK model, which characterized the influence of body weight and other patient covariates on exposure, has been developed. The PK profile of pembrolizumab is consistent with that of other humanized monoclonal antibodies, which typically have a low clearance and a limited volume of distribution. The distribution of exposures from the 200 mg fixed dose is predicted to considerably overlap those obtained with the 2 mg/kg dose and importantly will maintain individual patient exposures within the exposure range established in melanoma as associated with maximal clinical response. PK properties of pembrolizumab, and specifically the weight-dependency in clearance and volume of distribution are consistent with no meaningful advantage to weight-based dosing relative to fixed dosing.

In translating to other tumor indications, similarly flat exposure-response relationships for efficacy and safety as observed in subjects with melanoma can be expected, as the anti-tumor effect of pembrolizumab is driven through immune system activation rather than through a direct interaction with tumor cells, rendering it independent of the specific tumor type. In addition, available PK results in subjects with melanoma, NSCLC, and other tumor types support a lack of meaningful difference in PK exposures obtained at tested doses

among tumor types. Thus the 200 mg Q3W fixed-dose regimen is considered an appropriate fixed dose for other tumor indications as well.

A fixed-dose regimen will simplify the dosing regimen to be more convenient for physicians and to reduce potential for dosing errors. A fixed-dosing scheme will also reduce complexity in the logistical chain at treatment facilities and reduce wastage. The existing data suggest 200 mg Q3W as the appropriate dose for pembrolizumab.

As described in Section 1.1, Acerta Pharma has conducted a nonclinical study to evaluate the potential synergy of BTK inhibition with PD-1 blockade and has seen encouraging results which warrant testing the hypothesis in a clinical trial.

## 3.3 SELECTION OF STUDY POPULATION

## 3.3.1 Inclusion Criteria

Eligible subjects will be considered for inclusion in this study if they meet **all** of the following criteria:

####  Part 1

- 1) Diagnosis of non-GCB DLBCL or iNHL as documented by medical records and with histology based on criteria established by the WHO.
  - a) If the subject has DLBCL, it is characterized as de novo non-GCB DLBCL (Hans 2004; Choi 2009).
  - b) If the subject has iNHL, the histology shows one of the following subtypes:
    - i) FL Grade 1, 2, or 3a
    - ii) CLL/SLL
- 2) Prior treatment for lymphoid malignancy (applies to Part 1 and Part 2 of the protocol):
  - a) If the subject has DLBCL, there is no curative option with conventional therapy and the prior treatment included ≥1 prior combination chemoimmunotherapy regimen (e.g., anthracycline based therapy with rituximab).
  - b) If the subject has MCL or iNHL, the prior treatment comprised any of the following:
    - i) ≥1 regimen containing an anti-CD20 antibody administered for ≥2 doses, and/or
    - ii) ≥1 regimen containing ≥1 cytotoxic agent (e.g., bendamustine, chlorambucil, cyclophosphamide, cytarabine, doxorubicin) administered for ≥2 cycles, and/or

- iii) ≥1 regimen containing yttrium^90-ibritumomab tiuxetan (ZEVALIN®) or iodine-tositumomab (BEXXAR®).
- 3) Presence of radiographically measurable lymphadenopathy or extranodal lymphoid malignancy (defined as the presence of a ≥2.0-cm lesion as measured in the longest dimension by CT scan). Note: Not applicable to subjects with WM and MM.
- ANC ≥1.5×10^9/L or platelet count ≥100×10^9/L unless due to disease involvement in the bone marrow (Part 1 only).

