
 
≥1 regimen containing yttrium^90-ibritumomab tiuxetan (ZEVALIN®) or iodine-tositumomab (BEXXAR®).
 

 
Presence of radiographically measurable lymphadenopathy or extranodal lymphoid malignancy (defined as the presence of a ≥2.0 cm lesion, as measured in the longest dimension by computed tomography [CT] scan). Note: Not applicable to subjects with WM and MM.
 

 
Absolute neutrophil count (ANC) ≥1.5×10^9/L and platelet count ≥100×10^9/L unless due to disease involvement in the bone marrow (Part 1 only).
 

Part 2:

 
ANC ≥0.5×10^9/L and platelet count ≥50×10^9/L unless due to disease involvement in the bone marrow (Part 2 only).
 

Additional Part 2 disease entry criteria including those listed in Part 1 above:
• DLBCL (GCB): Confirmed diagnosis of DLBCL with disease characterized as GCB subtype by immunohistochemistry (Hans et al 2004; Choi et al 2009) and meeting the rest of the criteria as defined above, including characterization as de novo DLBCL.

 
If the subject has MCL, it is characterized by documentation of monoclonal B-cell that have a chromosome translocation t(11;14)(q13;q32) and/or overexpression of cyclin D1
 

• Richter's syndrome: Confirmed diagnosis of and biopsy-proven DLBCL due to Richter transformation and meeting the rest of the criteria as defined above.

 
WM: Confirmed diagnosis of WM, which has relapsed after, or been refractory to ≥1 prior therapy for WM, and is progressing at the time of study entry and meeting the rest of the criteria as defined above. Must be able to provide archival or newly obtained bone marrow aspirate/biopsy material for biomarker analysis.
 

 
MM: Confirmed diagnosis of MM, which has relapsed after, or been refractory to ≥3 prior therapies for MM, and is progressing at the time of study entry and meeting the rest of the criteria as defined above. Must be able to provide archival or newly obtained bone marrow aspirate/biopsy material for biomarker analysis.
 

 
Other B-cell malignancy (including but not limited to: Hodgkin's lymphoma, Burkitt lymphoma, marginal zone lymphomas, mediastinal large B-cell lymphoma, and hairy cell leukemia): Confirmed diagnosis of previously treated B-cell malignancy and meeting the rest of the criteria as defined above.
 

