##  Part 2

 ANC ≥0.5×10^9/L and platelet count ≥50×10^9/L unless due to disease involvement in the bone marrow (Part 2 only).

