## 3.7 ASSESSMENT OF DOSE-LIMITING TOXICITY

In Part 1 the first 6 subjects enrolled will be evaluated for DLT. The DLT review period is the first 6 weeks on treatment. A DLT will be defined as the occurrence of any of the following study-drug-related AEs (note: AEs clearly related to disease progression or the subject's current medical history and associated comorbidities will not be considered DLTs):

- 1. Any Grade ≥3 non-hematologic toxicity (except Grade 3 nausea, vomiting, or diarrhea that respond to supportive therapy)
- 2. Any of the following hematologic toxicities:
  - a. Grade 4 neutropenia lasting >7 days.
  - b. Grade 4 thrombocytopenia, or Grade 3 thrombocytopenia with bleeding, or any requirement for platelets transfusion.
  - c. Grade  $\geq$ 3 febrile neutropenia (temperature  $\geq$ 38.5°C).
  - d. Grade 4 anemia, unexplained by underlying disease.
- 3. Dosing delay due to toxicity for >28 consecutive days.

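### The Part 1 blood-count criterion joins ANC and platelets with *or* in Section 3.3.1 but with *and* in the synopsis; read literally, *or* leaves the second count without a floor in the stage that assesses DLTs.

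*Protocol*

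**What the plan says.** The Part 1 criterion in Protocol Section 3.3.1 asks for ANC ≥1.5×10⁹/L "or platelet count ≥100×10 9 /L unless due to disease involvement in the bone marrow (Part 1 only". The Study Synopsis, under Inclusion Criteria for Part 1, reads "Absolute neutrophil count (ANC) ≥1.5×10 9 /L and platelet count ≥100×10 9 /L unless due to disease involvement in the bone marrow (Part 1 only". The thresholds, marrow exception and restriction to Part 1 are identical; only the conjunction differs. Both are current text, and neither is said to prevail.

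For Part 2, Section 3.3.1 reads "ANC ≥0.5×10 9 /L and platelet count ≥50×10 9 /L unless due to disease involvement in the bone marrow (Part 2 only", and the synopsis also uses *and*.

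The hematologic DLTs in Section 3.7 include "Grade 4 neutropenia lasting >7 days" and "Grade 4 thrombocytopenia, or Grade 3 thrombocytopenia with bleeding, or any requirement for platelets transfusion". Section 3.7 counts only events related to study drug and sets aside those clearly due to progression, current medical history or comorbidity. Section 5.2 allows Part 1 to expand to up to 24 subjects if at most one DLT occurs among the six reviewed. Part 1 safety and preliminary efficacy then inform whether Parts 2 and 3 open.

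**The concern.** A criterion joined by *or* is met as soon as one half is met. A Part 1 subject with an adequate ANC therefore has no platelet minimum under Section 3.3.1, and one with adequate platelets has no ANC minimum. No other Part 1 criterion sets a numerical floor for either count. Part 1 carries the higher stated thresholds, yet read this way it can admit subjects whom the lower Part 2 floors would exclude.

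The same counts feed the DLT definition. If a subject enters with a count already in the listed range, a further fall or a platelet transfusion is hard to attribute: it may be put down to the drugs when it is not, or to the subject's history when the drugs contributed. With six subjects and a limit of one DLT, a single attribution can matter. The two texts also give different answers on whether a given subject was eligible, which affects the important protocol deviations in SAP Section 9.3.

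**Working it through.** **1. What each wording admits.** Take a subject without marrow involvement and apply each rule to four combinations chosen for illustration (units of 10⁹/L).

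| ANC | Platelets | Part 1, Section 3.3.1 (*or*: 1.5, 100) | Part 1, synopsis (*and*: 1.5, 100) | Part 2 (*and*: 0.5, 50) |
|---|---|---|---|---|
| 2.0 | 150 | eligible | eligible | eligible |
| 2.0 | 15 | eligible | not eligible | not eligible |
| 0.4 | 150 | eligible | not eligible | not eligible |
| 0.4 | 15 | not eligible | not eligible | not eligible |

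The two Part 1 texts disagree on the middle rows. Those subjects would also fail Part 2.

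**2. Link to the DLT list.** Section 3.8.1 puts Grade 4 neutropenia below 500/µL. An ANC of 0.4×10⁹/L is 400/µL, so the third-row subject already has a Grade 4 count at entry. The documents give no platelet cut-off for Grade 4. None is needed here, because *or* sets no platelet floor at all once the ANC is adequate.

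**3. The marrow exception.** Both wordings waive the thresholds when the low count is due to marrow disease. All four rows are then admissible under either wording. Resolving the conjunction bears only on cytopenia from other causes.

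**4. The plan's own gate.** The rule of at most 1 DLT in 6 agrees with the MTD definition in Section 5.2 (DLT in fewer than 33.3% of subjects): 1/6 = 16.7% passes and 2/6 = 33.3% does not.

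**5. How much one subject could matter.** The true DLT rates p and the one-subject scenarios are assumptions, not figures from the documents. DLTs are taken as independent.

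- Rule as planned: P(X ≤ 1), X ~ Bin(6, p) = (1−p)⁶ + 6p(1−p)⁵.
- One subject's baseline cytopenia wrongly counted as a DLT: the other five must have none, (1−p)⁵.
- One subject can register no DLT: P(X ≤ 1), X ~ Bin(5, p) = (1−p)⁵ + 5p(1−p)⁴.

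At p = 0.20 these are 0.262 + 0.393 = 0.655; 0.328; and 0.328 + 0.410 = 0.737 (from unrounded terms).

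| p | As planned | One wrongly counted | One fully masked |
|---|---|---|---|
| 10% | 0.886 | 0.590 | 0.919 |
| 20% | 0.655 | 0.328 | 0.737 |
| 30% | 0.420 | 0.168 | 0.528 |
| 33.3% | 0.351 | 0.132 | 0.461 |

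The last column is an outer limit. A subject with one low count can still register DLTs in the other lineages, non-hematologic toxicity and dosing delay, so partial masking falls between the first and third columns of probabilities.

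**The case against.** The strongest reply is that the protocol already guards against miscounting. Section 3.7 requires relation to study drug and excludes events clearly due to medical history. Section 6.1.1 says a pre-existing condition is not an adverse event unless it worsens in severity, frequency or character, so an unchanged baseline cytopenia cannot be a DLT. Criterion 24 requires recovery to Grade ≤1 or baseline from prior-therapy toxicity, and exclusion 2 lets the investigator bar organ dysfunction that endangers the subject or the study outcomes. Section 3.3.3 permits replacement to complete the DLT assessment. Enrolment closed in May 2017 (Section 5.1), so rewording cannot change who entered.

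Most of this stands, and it limits what can be claimed. It does not remove the contradiction. The safeguards rest on judgement when a low count worsens. Among the hematologic DLTs, only Grade 4 anemia has its own carve-out for underlying disease. Criterion 24 covers only prior-therapy toxicity and accepts baseline. Section 3.3.3 does not say whether a subject who is uninformative for one lineage is replaced.

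A reader might infer three stronger things:

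- *The DLT gate was decided wrongly.* The documents do not show that any of the six subjects had such a cytopenia.
- *Each such subject costs one sixth (17%) of the hematologic denominator.* Replacement is allowed, and under *or* at least one of the two counts is adequate, so the subject stays assessable elsewhere.
- *The synopsis wording is correct and should be applied to all past enrolment.* Agreement with Part 2 suggests an intention, but nothing shows which wording governed Part 1. Imposing one afterwards could label a subject enrolled in line with Section 3.3.1 as a deviation because of a drafting conflict.

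**Conclusion.** The criterion is wrong as written, because two current passages of the protocol give different eligibility rules for the same subjects. Under the literal *or*, and for cytopenia not due to marrow disease, the DLT stage could admit a subject already in a range that Section 3.7 lists. The consequence is possible misattribution or masking of a hematologic DLT in a six-subject review, plus inconsistent classification of eligibility deviations.

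The size is conditional. One misattributed subject would move the chance of passing appreciably (0.655 to 0.328 at an assumed 20% rate), and one masked subject by less (to at most 0.737). Both figures assume that such a subject was among the six and was misjudged, which the documents neither show nor rule out. No view is taken here on which eligibility rule is right.

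**What to change.** 1. Reconcile the Part 1 criterion in Section 3.3.1 with the synopsis, and have the sponsor state which wording governed Part 1 enrolment.
2. Classify Part 1 eligibility deviations under SAP Section 9.3 consistently by that wording.
3. Add a listing for the six DLT-review subjects with baseline ANC, baseline platelet count, marrow involvement and DLT outcome. SAP Section 9.4.2 does not include the counts among baseline characteristics, SAP Section 9.7 specifies no DLT summary, and the by-subject laboratory listings in Section 9.7.2 do not set counts beside DLT outcome. Marrow involvement belongs in the listing because the exception admits cytopenic subjects whichever wording applied.

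The cost is a small text correction and a six-row listing. A few Part 1 subjects may change deviation status.
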